**14.3.1.5: TEAEs, which are injection site reactions, Safety analysis set**

→ Repetition of table 14.3.1.2 with different selection of the AE analysis dataset.

**14.3.1.6: Study drug-related TEAEs by system organ class and preferred term, Safety analysis set**

→ Repetition of table 14.3.1.2 with different selection of the AE analysis dataset.

14.3.1.7: TEAEs by system organ class and preferred term and causal relationship, Safety analysis set

System organ class Preferred term	dasiglucagon (N=xxx)		Placebo (N=xxx)		GlucaGen (N=xxx)	
	Related 	Not Related 	Related 	Not Related 	Related 	Not Related 
Any adverse event	xx ( xx.x) xx	xx ( xx.x) xx	xx ( xx.x) xx	xx ( xx.x) xx	xx ( xx.x) xx	xx ( xx.x) xx
SOC class 1						
PT Term 1	xx ( xx.x) xx	xx ( xx.x) xx	xx ( xx.x) xx	xx ( xx.x) xx	xx ( xx.x) xx	xx ( xx.x) xx
PT Term 2	xx ( xx.x) xx	xx ( xx.x) xx	xx ( xx.x) xx	xx ( xx.x) xx	xx ( xx.x) xx	xx ( xx.x) xx
PT Term 3	xx ( xx.x) xx	xx ( xx.x) xx	xx ( xx.x) xx	xx ( xx.x) xx	xx ( xx.x) xx	xx ( xx.x) xx
PT Term xx	xx ( xx.x) xx	xx ( xx.x) xx	xx ( xx.x) xx	xx ( xx.x) xx	xx ( xx.x) xx	xx ( xx.x) xx
SOC class 2						
PT Term 1	xx ( xx.x) xx	xx ( xx.x) xx	xx ( xx.x) xx	xx ( xx.x) xx	xx ( xx.x) xx	xx ( xx.x) xx
PT Term 2	xx ( xx.x) xx	xx ( xx.x) xx	xx ( xx.x) xx	xx ( xx.x) xx	xx ( xx.x) xx	xx ( xx.x) xx
PT Term 3	xx ( xx.x) xx	xx ( xx.x) xx	xx ( xx.x) xx	xx ( xx.x) xx	xx ( xx.x) xx	xx ( xx.x) xx
PT Term xx	xx ( xx.x) xx	xx ( xx.x) xx	xx ( xx.x) xx	xx ( xx.x) xx	xx ( xx.x) xx	xx ( xx.x) xx

---

Note: At each level of summation (SOC class, preferred name) patients reporting more than 1 event are counted only once for the patient count.

[1] Includes all events reported as 'Possible', 'Probable' or missing relationship.

[2] Includes all events reported as 'Not related or 'Unlikely'.

Table is sorted by descending subject count on the PT level in the dasiglucagon group.

Percentages are based on total no. of subjects in each treatment group.

PROGRAM SOURCE:###, DATA CUT OFF DATE: ddmmyyyy

RUN DATE: ddmmyyy hh:mm CET

14.3.1.8: TEAEs by system organ class and preferred term and severity, Safety analysis set

System organ class Preferred term	dasiglucagon (N=xxx)			Placebo (N=xxx)			Glucagen (N=xxx)		
	Mild	Moderate	Severe	Mild	Moderate	Severe	Mild	Moderate	Severe
Any adverse event	xx ( xx.x) xx	xx ( xx.x) xx	xx ( xx.x) xx	xx ( xx.x) xx	xx ( xx.x) xx	xx ( xx.x) xx	xx ( xx.x) xx	xx ( xx.x) xx	xx ( xx.x) xx
SOC class 1									
PT Term 1	xx ( xx.x) xx	xx ( xx.x) xx	xx ( xx.x) xx	xx ( xx.x) xx	xx ( xx.x) xx	xx ( xx.x) xx	xx ( xx.x) xx	xx ( xx.x) xx	xx ( xx.x) xx
PT Term 2	xx ( xx.x) xx	xx ( xx.x) xx	xx ( xx.x) xx	xx ( xx.x) xx	xx ( xx.x) xx	xx ( xx.x) xx	xx ( xx.x) xx	xx ( xx.x) xx	xx ( xx.x) xx
PT Term 3	xx ( xx.x) xx	xx ( xx.x) xx	xx ( xx.x) xx	xx ( xx.x) xx	xx ( xx.x) xx	xx ( xx.x) xx	xx ( xx.x) xx	xx ( xx.x) xx	xx ( xx.x) xx
PT Term xx	xx ( xx.x) xx	xx ( xx.x) xx	xx ( xx.x) xx	xx ( xx.x) xx	xx ( xx.x) xx	xx ( xx.x) xx	xx ( xx.x) xx	xx ( xx.x) xx	xx ( xx.x) xx
SOC class 2									
PT Term 1	xx ( xx.x) xx	xx ( xx.x) xx	xx ( xx.x) xx	xx ( xx.x) xx	xx ( xx.x) xx	xx ( xx.x) xx	xx ( xx.x) xx	xx ( xx.x) xx	xx ( xx.x) xx
PT Term 2	xx ( xx.x) xx	xx ( xx.x) xx	xx ( xx.x) xx	xx ( xx.x) xx	xx ( xx.x) xx	xx ( xx.x) xx	xx ( xx.x) xx	xx ( xx.x) xx	xx ( xx.x) xx
PT Term 3	xx ( xx.x) xx	xx ( xx.x) xx	xx ( xx.x) xx	xx ( xx.x) xx	xx ( xx.x) xx	xx ( xx.x) xx	xx ( xx.x) xx	xx ( xx.x) xx	xx ( xx.x) xx
PT Term xx	xx ( xx.x) xx	xx ( xx.x) xx	xx ( xx.x) xx	xx ( xx.x) xx	xx ( xx.x) xx	xx ( xx.x) xx	xx ( xx.x) xx	xx ( xx.x) xx	xx ( xx.x) xx

Note: At each level of summation (SOC class, preferred name) patients reporting more than 1 event are counted only once for the patient count.  
Table is sorted by descending subject count on the PT level in the dasiglucagon group.  
Percentages are based on total no. of subjects in each treatment group.

PROGRAM SOURCE:###, DATA CUT OFF DATE: ddmmmyyyy

RUN DATE: ddmmmyyy hh:mm CET

**14.3.1.9: SAEs by system organ class and preferred term, Safety analysis set**

→ Repetition of table 14.3.1.2 with different selection of the AE analysis dataset.

Zealand Pharma A/S  
Protocol Number: ZP4207-17086

Clinical Study Report Section 14  
Page 1 of x

**14.3.1.10: Special search category TEAEs, Safety analysis set**

→ Repetition of table 14.3.1.2 with different selection of the AE analysis dataset.

14.3.2: Listings of deaths, other serious and significant adverse events, Safety analysis set

Please refer to listing 16.2.7.4.

*Programmer Note: Create a empty table with that reference as message*

14.3.3: Narratives of deaths, other serious and certain other significant adverse events, Safety analysis set

Please refer to listing 16.2.7.4.

*Programmer Note: Create a empty table with that reference as message*

14.3.4.1: Insulin administration prior to the hypoglycemia induction procedure, Safety analysis set

	dasiglucagon (N=xxx)	Placebo (N=xxx)	GlucaGen (N=xxx)	Total (N=xxx)
Is the subject using multiple daily injections?				
No	n ( xx.x%)	n ( xx.x%)	n ( xx.x%)	n ( xx.x%)
Yes	n ( xx.x%)	n ( xx.x%)	n ( xx.x%)	n ( xx.x%)
Missing	n	n	n	n
Has the subject taken insulin NPH?				
No	n ( xx.x%)	n ( xx.x%)	n ( xx.x%)	n ( xx.x%)
Yes	n ( xx.x%)	n ( xx.x%)	n ( xx.x%)	n ( xx.x%)
Missing	n	n	n	n
Is the subject using an insulin pump?				
No	n ( xx.x%)	n ( xx.x%)	n ( xx.x%)	n ( xx.x%)
Yes	n ( xx.x%)	n ( xx.x%)	n ( xx.x%)	n ( xx.x%)
Missing	n	n	n	n
Was insulin glulisine (Apidra) administered in the last 5 hours prior to initiation of the hypoglycemic induction procedure?				
No	n ( xx.x%)	n ( xx.x%)	n ( xx.x%)	n ( xx.x%)
Yes	n ( xx.x%)	n ( xx.x%)	n ( xx.x%)	n ( xx.x%)
Missing	n	n	n	n

PROGRAM SOURCE:###, DATA CUT OFF DATE: ddmmmyyy

RUN DATE: ddmyyy hh:mm CET

14.3.4.2: Hypoglycemia induction procedure, Safety analysis set

	dasiglucagon (N=xxx)	Placebo (N=xxx)	GlucaGen (N=xxx)	Total (N=xxx)
Was the hypoglycemia induction procedure performed?				
No	n ( xx.x%)	n ( xx.x%)	n ( xx.x%)	n ( xx.x%)
Yes	n ( xx.x%)	n ( xx.x%)	n ( xx.x%)	n ( xx.x%)
Missing	n	n	n	n
Total amount of insulin administered to induce hypoglycemia [IU]				
n	xx	xx	xx	xx
Mean (SD)	xx.x (xx.xx)	xx.x (xx.xx)	xx.x (xx.xx)	xx.x (xx.xx)
Median	xx.x	xx.x	xx.x	xx.x
Min, Max	xx, xx	xx, xx	xx, xx	xx, xx
Total amount of glucose administered during the induction procedure [mL]				
n	xx	xx	xx	xx
Mean (SD)	xx.x (xx.xx)	xx.x (xx.xx)	xx.x (xx.xx)	xx.x (xx.xx)
Median	xx.x	xx.x	xx.x	xx.x
Min, Max	xx, xx	xx, xx	xx, xx	xx, xx

PROGRAM SOURCE:###, DATA CUT OFF DATE: ddmmyyyy

RUN DATE: ddmmyyy hh:mm CET

Zealand Pharma A/S  
ZP4207-17086 (ZEA-DNK-02170)

Statistical Analysis Plan  
16 August 2019

Zealand Pharma A/S  
Protocol Number: ZP4207-17086

Clinical Study Report Section 14  
Page 1 of 1

14.3.4.3: Trial medication, Safety analysis set

	dasiglucagon (N=xxx)	Placebo (N=xxx)	GlucaGen (N=xxx)	Total (N=xxx)
Was the trial medication administered?				
No	n ( xx.x%)	n ( xx.x%)	n ( xx.x%)	n ( xx.x%)
Yes	n ( xx.x%)	n ( xx.x%)	n ( xx.x%)	n ( xx.x%)
Missing	n	n	n	n

PROGRAM SOURCE:###, DATA CUT OFF DATE: ddmmyyyy

RUN DATE: ddmmyyy hh:mm CET

14.3.4.4: Post-treatment rescue glucose infusion, Safety analysis set

	dasiglucagon (N=xxx)	Placebo (N=xxx)	GlucaGen (N=xxx)	Total (N=xxx)
Was glucose given for rescue?				
No	n ( xx.x%)	n ( xx.x%)	n ( xx.x%)	n ( xx.x%)
Yes	n ( xx.x%)	n ( xx.x%)	n ( xx.x%)	n ( xx.x%)
Missing	n	n	n	n
Time to first IV glucose infusion [min]				
Mean (SD)	n	xx	xx	xx
Median	Mean (SD)	xx.x (xx.xx)	xx.x (xx.xx)	xx.x (xx.xx)
Min, Max	Median	xx.x	xx.x	xx.x
	Min, Max	xx, xx	xx, xx	xx, xx

PROGRAM SOURCE:###, DATA CUT OFF DATE: ddmmmyyyy

RUN DATE: ddmyyy hh:mm CET

14.3.5.1.1: ECG, overall interpretation, Safety analysis set

Visit	Time Point	Result	dasiglucagon (N=xxx)	Placebo (N=xxx)	GlucaGen (N=xxx)	Total (N=xxx)
Screening		NORMAL	n ( xx.x%)	n ( xx.x%)	n ( xx.x%)	n ( xx.x%)
		ABNORMAL / NOT CLIN. SIG.	n ( xx.x%)	n ( xx.x%)	n ( xx.x%)	n ( xx.x%)
		ABNORMAL / CLIN. SIG.	n ( xx.x%)	n ( xx.x%)	n ( xx.x%)	n ( xx.x%)
Dosing	Pre-dose	NORMAL	n ( xx.x%)	n ( xx.x%)	n ( xx.x%)	n ( xx.x%)
		ABNORMAL / NOT CLIN. SIG.	n ( xx.x%)	n ( xx.x%)	n ( xx.x%)	n ( xx.x%)
		ABNORMAL / CLIN. SIG.	n ( xx.x%)	n ( xx.x%)	n ( xx.x%)	n ( xx.x%)
Dosing	20min post dose	NORMAL	n ( xx.x%)	n ( xx.x%)	n ( xx.x%)	n ( xx.x%)
		ABNORMAL / NOT CLIN. SIG.	n ( xx.x%)	n ( xx.x%)	n ( xx.x%)	n ( xx.x%)
		ABNORMAL / CLIN. SIG.	n ( xx.x%)	n ( xx.x%)	n ( xx.x%)	n ( xx.x%)
Dosing	35min post dose	NORMAL	n ( xx.x%)	n ( xx.x%)	n ( xx.x%)	n ( xx.x%)
		ABNORMAL / NOT CLIN. SIG.	n ( xx.x%)	n ( xx.x%)	n ( xx.x%)	n ( xx.x%)
		ABNORMAL / CLIN. SIG.	n ( xx.x%)	n ( xx.x%)	n ( xx.x%)	n ( xx.x%)
Dosing	45min post dose	NORMAL	n ( xx.x%)	n ( xx.x%)	n ( xx.x%)	n ( xx.x%)
		ABNORMAL / NOT CLIN. SIG.	n ( xx.x%)	n ( xx.x%)	n ( xx.x%)	n ( xx.x%)
		ABNORMAL / CLIN. SIG.	n ( xx.x%)	n ( xx.x%)	n ( xx.x%)	n ( xx.x%)
Dosing	60min post dose	NORMAL	n ( xx.x%)	n ( xx.x%)	n ( xx.x%)	n ( xx.x%)
		ABNORMAL / NOT CLIN. SIG.	n ( xx.x%)	n ( xx.x%)	n ( xx.x%)	n ( xx.x%)
		ABNORMAL / CLIN. SIG.	n ( xx.x%)	n ( xx.x%)	n ( xx.x%)	n ( xx.x%)
Dosing	300min post dose	NORMAL	n ( xx.x%)	n ( xx.x%)	n ( xx.x%)	n ( xx.x%)
		ABNORMAL / NOT CLIN. SIG.	n ( xx.x%)	n ( xx.x%)	n ( xx.x%)	n ( xx.x%)
		ABNORMAL / CLIN. SIG.	n ( xx.x%)	n ( xx.x%)	n ( xx.x%)	n ( xx.x%)

PROGRAM SOURCE:###, DATA CUT OFF DATE: ddmmyyyy

RUN DATE: ddmmyyy hh:mm CET

Zealand Pharma A/S  
ZP4207-17086 (ZEA-DNK-02170)

Statistical Analysis Plan  
16 August 2019

Zealand Pharma A/S  
Protocol Number: ZP4207-17086

Clinical Study Report Section 14  
Page 2 of 2

14.3.5.1.1: ECG, overall interpretation, Safety analysis set

Visit	Time Point	Result	dasiglucagon (N=xxx)	Placebo (N=xxx)	GlucaGen (N=xxx)	Total (N=xxx)
Follow up		NORMAL	n ( xx.x%)	n ( xx.x%)	n ( xx.x%)	n ( xx.x%)
		ABNORMAL / NOT CLIN. SIG.	n ( xx.x%)	n ( xx.x%)	n ( xx.x%)	n ( xx.x%)
		ABNORMAL / CLIN. SIG.	n ( xx.x%)	n ( xx.x%)	n ( xx.x%)	n ( xx.x%)

PROGRAM SOURCE:###, DATA CUT OFF DATE: ddmmyyyy

RUN DATE: ddmmyy hh:mm CET

14.3.5.1.2: ECG, descriptive statistics of all ECG parameters, Safety analysis set

Parameter	Visit/ TimePoint	Result	dasiglucagon (N=xxx)	Placebo (N=xxx)	Glucagen (N=xxx)	Total (N=xxx)
Mean heart rate [bpm]	Screening	n	xx	xx	xx	xx
		Mean (SD)	xx.x (xx.xx)	xx.x (xx.xx)	xx.x (xx.xx)	xx.x (xx.xx)
		Median	xx.x	xx.x	xx.x	xx.x
		Min, Max	xx, xx	xx, xx	xx, xx	xx, xx
	Dosing/ Pre-dose	n	xx	xx	xx	xx
		Mean (SD)	xx.x (xx.xx)	xx.x (xx.xx)	xx.x (xx.xx)	xx.x (xx.xx)
		Median	xx.x	xx.x	xx.x	xx.x
		Min, Max	xx, xx	xx, xx	xx, xx	xx, xx
	Dosing/20 min after dosing	n	xx	xx	xx	xx
		Mean (SD)	xx.x (xx.xx)	xx.x (xx.xx)	xx.x (xx.xx)	xx.x (xx.xx)
		Median	xx.x	xx.x	xx.x	xx.x
		Min, Max	xx, xx	xx, xx	xx, xx	xx, xx
...						
Follow up	n	xx	xx	xx	xx	
	Mean (SD)	xx.x (xx.xx)	xx.x (xx.xx)	xx.x (xx.xx)	xx.x (xx.xx)	
	Median	xx.x	xx.x	xx.x	xx.x	
	Min, Max	xx, xx	xx, xx	xx, xx	xx, xx	

PROGRAM SOURCE:###, DATA CUT OFF DATE: ddmmmyyy

RUN DATE: ddmmmyyy hh:mm CET

*Programmer Note: This table is continued for each of the following ECG parameter: PR Interval Aggregate [msec], QRS Duration Aggregate[msec], QT Interval Aggregate[msec], QTcF Interval Aggregate[msec]*

Zealand Pharma A/S  
Protocol Number: ZP4207-17086

Clinical Study Report Section 14  
Page 1 of x

14.3.5.1.3: ECG, categorical analysis of QTc results, Safety analysis set

Visit	Time Point	Result	dasiglucagon (N=xxx)	Placebo (N=xxx)	GlucaGen (N=xxx)	Total (N=xxx)
Screening		QTcF values of >450 ms	n ( xx.x%)	n ( xx.x%)	n ( xx.x%)	n ( xx.x%)
		QTcF values of >480 ms	n ( xx.x%)	n ( xx.x%)	n ( xx.x%)	n ( xx.x%)
		QTcF values of >500 ms	n ( xx.x%)	n ( xx.x%)	n ( xx.x%)	n ( xx.x%)
Dosing	Pre-dose	QTcF values of >450 ms	n ( xx.x%)	n ( xx.x%)	n ( xx.x%)	n ( xx.x%)
		QTcF values of >480 ms	n ( xx.x%)	n ( xx.x%)	n ( xx.x%)	n ( xx.x%)
		QTcF values of >500 ms	n ( xx.x%)	n ( xx.x%)	n ( xx.x%)	n ( xx.x%)
Dosing	20min post dose	QTcF values of >450 ms	n ( xx.x%)	n ( xx.x%)	n ( xx.x%)	n ( xx.x%)
		QTcF values of >480 ms	n ( xx.x%)	n ( xx.x%)	n ( xx.x%)	n ( xx.x%)
		QTcF values of >500 ms	n ( xx.x%)	n ( xx.x%)	n ( xx.x%)	n ( xx.x%)
...						
Follow up		QTcF values of >450 ms	n ( xx.x%)	n ( xx.x%)	n ( xx.x%)	n ( xx.x%)
		QTcF values of >480 ms	n ( xx.x%)	n ( xx.x%)	n ( xx.x%)	n ( xx.x%)
		QTcF values of >500 ms	n ( xx.x%)	n ( xx.x%)	n ( xx.x%)	n ( xx.x%)

PROGRAM SOURCE:###, DATA CUT OFF DATE: ddmmmyyyy

RUN DATE: ddmmmyyy hh:mm CET

14.3.5.1.4: ECG, categorical analysis of QTc results, change from baseline, Safety analysis set

Visit	Time Point	Result	dasiglucagon (N=xxx)	Placebo (N=xxx)	GlucaGen (N=xxx)	Total (N=xxx)
Dosing	20min post dose	QTcF CFB >30 ms QTcF CFB >60 ms	n ( xx.x%) n ( xx.x%)	n ( xx.x%) n ( xx.x%)	n ( xx.x%) n ( xx.x%)	n ( xx.x%) n ( xx.x%)
Dosing	35min post dose	QTcF CFB >30 ms QTcF CFB >60 ms	n ( xx.x%) n ( xx.x%)	n ( xx.x%) n ( xx.x%)	n ( xx.x%) n ( xx.x%)	n ( xx.x%) n ( xx.x%)
...						
Follow up		QTcF CFB >30 ms QTcF CFB >60 ms	n ( xx.x%) n ( xx.x%)	n ( xx.x%) n ( xx.x%)	n ( xx.x%) n ( xx.x%)	n ( xx.x%) n ( xx.x%)

PROGRAM SOURCE:###, DATA CUT OFF DATE: ddmmyyyy

RUN DATE: ddmmyyyy hh:mm CET

*Programmer Note: Baseline is the pre-dose result at visit 1 Screening*

14.3.5.2.1: Hematology, Safety analysis set

Treatment	Visit	n	Mean	Median	SD	Min	Max	CFB -Mean	CFB- SD	Below reference range n(%)	Within reference range n(%)	Above reference range n(%)
Laboratory parameter test name 1												
dasiglucagon	Screening	xx	xx.xx	xx.xx	xx.xxx	xx.x	xx.x	-	-	n ( xx.x%)	n ( xx.x%)	n ( xx.x%)
	Follow up	xx	xx.xx	xx.xx	xx.xxx	xx.x	xx.x	xx.xx	xx.xxx	n ( xx.x%)	n ( xx.x%)	n ( xx.x%)
Placebo	Screening	xx	xx.xx	xx.xx	xx.xxx	xx.x	xx.x	-	-	n ( xx.x%)	n ( xx.x%)	n ( xx.x%)
	Follow up	xx	xx.xx	xx.xx	xx.xxx	xx.x	xx.x	xx.xx	xx.xxx	n ( xx.x%)	n ( xx.x%)	n ( xx.x%)
Glucagon	Screening	xx	xx.xx	xx.xx	xx.xxx	xx.x	xx.x	-	-	n ( xx.x%)	n ( xx.x%)	n ( xx.x%)
	Follow up	xx	xx.xx	xx.xx	xx.xxx	xx.x	xx.x	xx.xx	xx.xxx	n ( xx.x%)	n ( xx.x%)	n ( xx.x%)
Total	Screening	xx	xx.xx	xx.xx	xx.xxx	xx.x	xx.x	-	-	n ( xx.x%)	n ( xx.x%)	n ( xx.x%)
	Follow up	xx	xx.xx	xx.xx	xx.xxx	xx.x	xx.x	xx.xx	xx.xxx	n ( xx.x%)	n ( xx.x%)	n ( xx.x%)
Laboratory parameter test name 2												
dasiglucagon	Screening	xx	xx.xx	xx.xx	xx.xxx	xx.x	xx.x	-	-	n ( xx.x%)	n ( xx.x%)	n ( xx.x%)
	Follow up	xx	xx.xx	xx.xx	xx.xxx	xx.x	xx.x	xx.xx	xx.xxx	n ( xx.x%)	n ( xx.x%)	n ( xx.x%)
Placebo	Screening	xx	xx.xx	xx.xx	xx.xxx	xx.x	xx.x	-	-	n ( xx.x%)	n ( xx.x%)	n ( xx.x%)
	Follow up	xx	xx.xx	xx.xx	xx.xxx	xx.x	xx.x	xx.xx	xx.xxx	n ( xx.x%)	n ( xx.x%)	n ( xx.x%)
Glucagon	Screening	xx	xx.xx	xx.xx	xx.xxx	xx.x	xx.x	-	-	n ( xx.x%)	n ( xx.x%)	n ( xx.x%)
	Follow up	xx	xx.xx	xx.xx	xx.xxx	xx.x	xx.x	xx.xx	xx.xxx	n ( xx.x%)	n ( xx.x%)	n ( xx.x%)
Total	Screening	xx	xx.xx	xx.xx	xx.xxx	xx.x	xx.x	-	-	n ( xx.x%)	n ( xx.x%)	n ( xx.x%)
	Follow up	xx	xx.xx	xx.xx	xx.xxx	xx.x	xx.x	xx.xx	xx.xxx	n ( xx.x%)	n ( xx.x%)	n ( xx.x%)
...												

PROGRAM SOURCE:###, DATA CUT OFF DATE: ddmmyyyy

RUN DATE: ddmmyyyy hh:mm CET

*Programmer Note: Each laboratory test parameter is either displayed one per page or as shown here two on 1 page if possible.*

14.3.5.2.2: Clinical chemistry, Safety analysis set

---

→ Repetition of table 14.3.5.2.1 with different selection of the lab analysis dataset.

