### 14.3.2 Adverse event tables

In addition, frequency tables will be prepared by MedDRA terms (system organ class, preferred term) showing the following:

1. All TEAEs
2. TEAEs, which are AESIs
3. TEAEs, which are an other important event
4. TEAEs, which are injection site reactions based on investigator assessment in CRF
5. Study-drug related TEAEs
6. TEAEs by causal relationship to study drug
7. TEAEs by severity
8. Serious TEAEs (SAEs)
9. Special search category TEAEs

The analysis of AEs will include summary tables displaying counts and percentages of patients experiencing AEs by system organ class and preferred term. If a patient has more than 1 AE which codes to the same preferred term, the patient will be counted only once for that preferred term. The total number of events documented per system order class and preferred term will also be displayed. Summaries will be ordered by descending order of incidence of system organ class and preferred term within each system organ class based on the frequency (proportion of patients) in the dasiglucagon group.

The special search category should include the following MedDRA tems:

Events of hypoglycemia

- SMQ Hypoglycemia (narrow)

Hemodynamic events

- Zealand custom search
- External file with PT to be provided by pharmacovigilance

Allergic reactions

- SMQ: Hypersensitivity (narrow)

Events related to QT interval prolongation

- SMQ: Torsade de pointes/QT prolongation (broad)

Renal disorders

- SMQ: Acute renal failure (broad)

Hepatic disorders

- SMQ: Drug related hepatic disorders (broad)

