PROGRAM SOURCE:###, DATA CUT OFF DATE: ddmmmyyy

RUN DATE: ddmmyy hh:mm CET

14.3.1.1: Overall summary of adverse events, Safety analysis set

	Number of Subjects (%) Event Count			
	dasiglucagon (N=xxx)	Placebo (N=xxx)	GlucaGen (N=xxx)	Total (N=xxx)
Adverse events during screening	xx ( xx.x) xx	xx ( xx.x) xx	xx ( xx.x) xx	xx ( xx.x) xx
Treatment-emergent AEs (TEAEs)	xx ( xx.x) xx	xx ( xx.x) xx	xx ( xx.x) xx	xx ( xx.x) xx
TEAEs, which are adverse events of special interest (AESIs)	xx ( xx.x) xx	xx ( xx.x) xx	xx ( xx.x) xx	xx ( xx.x) xx
TEAEs, which are another important event	xx ( xx.x) xx	xx ( xx.x) xx	xx ( xx.x) xx	xx ( xx.x) xx
TEAEs, which are injection site reactions	xx ( xx.x) xx	xx ( xx.x) xx	xx ( xx.x) xx	xx ( xx.x) xx
Study drug-related TEAEs 	xx ( xx.x) xx	xx ( xx.x) xx	xx ( xx.x) xx	xx ( xx.x) xx
Serious TEAEs (SAEs)	xx ( xx.x) xx	xx ( xx.x) xx	xx ( xx.x) xx	xx ( xx.x) xx
Study drug-related serious TEAEs	xx ( xx.x) xx	xx ( xx.x) xx	xx ( xx.x) xx	xx ( xx.x) xx
Deaths	xx ( xx.x) xx	xx ( xx.x) xx	xx ( xx.x) xx	xx ( xx.x) xx
...				

 Study drug-related TEAEs: TEAEs which were assessed by the investigator as possibly related or probably related, or without assessment of relationship.  
Table is based on number of verbatims.  
Patients reporting more than 1 event are counted only once for the patient count.  
Percentages are based on total no. of subjects in each treatment group

14.3.1.2: TEAEs by system organ class and preferred term, Safety analysis set

System organ class Preferred term	Number of Subjects (%) Event Count			Total (N=xxx)
	dasiglucagon (N=xxx)	Placebo (N=xxx)	GlucaGen (N=xxx)	
Any adverse event	xx ( xx.x) xx	xx ( xx.x) xx	xx ( xx.x) xx	xx ( xx.x) xx
SOC class 1				
PT Term 1	xx ( xx.x) xx	xx ( xx.x) xx	xx ( xx.x) xx	xx ( xx.x) xx
PT Term 2	xx ( xx.x) xx	xx ( xx.x) xx	xx ( xx.x) xx	xx ( xx.x) xx
PT Term 3	xx ( xx.x) xx	xx ( xx.x) xx	xx ( xx.x) xx	xx ( xx.x) xx
PT Term xx	xx ( xx.x) xx	xx ( xx.x) xx	xx ( xx.x) xx	xx ( xx.x) xx
SOC class 2				
PT Term 1	xx ( xx.x) xx	xx ( xx.x) xx	xx ( xx.x) xx	xx ( xx.x) xx
PT Term 2	xx ( xx.x) xx	xx ( xx.x) xx	xx ( xx.x) xx	xx ( xx.x) xx
PT Term 3	xx ( xx.x) xx	xx ( xx.x) xx	xx ( xx.x) xx	xx ( xx.x) xx
PT Term xx	xx ( xx.x) xx	xx ( xx.x) xx	xx ( xx.x) xx	xx ( xx.x) xx
SOC class xx				
PT Term 1	xx ( xx.x) xx	xx ( xx.x) xx	xx ( xx.x) xx	xx ( xx.x) xx
PT Term 2	xx ( xx.x) xx	xx ( xx.x) xx	xx ( xx.x) xx	xx ( xx.x) xx

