PT Term 3	xx ( xx.x) xx	xx ( xx.x) xx	xx ( xx.x) xx	xx ( xx.x) xx
PT Term xx	xx ( xx.x) xx	xx ( xx.x) xx	xx ( xx.x) xx	xx ( xx.x) xx
...				

Note: At each level of summation (SOC class, preferred name) patients reporting more than 1 event are counted only once for the patient count.  
Table is sorted by descending subject count on the PT level in the dasiglucagon group.  
Percentages are based on total no. of subjects in each treatment group

PROGRAM SOURCE:###, DATA CUT OFF DATE: ddmmyyyy

RUN DATE: ddmmyy hh:mm CET

14.3.1.3: TEAEs of special interest by system organ class and preferred term, Safety analysis set

→ Repetition of table 14.3.1.2 with different selection of the AE analysis dataset.

14.3.1.4: Other important TEAEs by system organ class and preferred term, Safety analysis set

→ Repetition of table 14.3.1.2 with different selection of the AE analysis dataset.

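### Table 14.3.1.10 has no row per special search, so no planned summary table gives the number of children with an allergic, QT, renal, hepatic or searched hemodynamic event

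*SAP*

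**What the plan says.** SAP 14.3.2 announces that "frequency tables will be prepared by MedDRA terms (system organ class, preferred term) showing the following". The special-search events are the ninth and last item of that list. The searches are then introduced with "The special search category should include the following MedDRA tems", followed by nine headings: hypoglycemia, hemodynamic events, allergic reactions, QT prolongation, renal disorders, hepatic disorders, medication errors, rare events and injection site reactions. Six use a standardised MedDRA query. Three (hemodynamic, rare events, injection site) use sponsor term lists held in external files.

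Appendix C lists one table for all of this, 14.3.1.10, with no comment. Appendix D titles it "14.3.1.10: Special search category TEAEs, Safety analysis set" and specifies it in one line: "Repetition of table 14.3.1.2 with different selection of the AE analysis dataset".

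The parent shell is "14.3.1.2: TEAEs by system organ class and preferred term, Safety analysis set". It has a row for any adverse event, then SOC headings with PT rows beneath. The shell prints patients, percent and event count. Its footnote sets the counting rule: "At each level of summation (SOC class, preferred name) patients reporting more than 1 event are counted only once for the patient count".

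**The concern.** A search of this kind puts different preferred terms under one medical question, for example whether a child had any allergic-type reaction. The natural summary is the number of children with at least one event in the category, by arm. An SOC/PT layout breaks the category up again: each term goes back under its own SOC, next to terms selected by other searches, and nothing marks which search selected it. For the three sponsor-defined searches, the SAP does not let a reader work out which PT belongs where.

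At stake is the readability of a descriptive safety summary. Arms are small (20 dasiglucagon, 10 placebo and 10 GlucaGen in SAP Section 5), so a category could be made up of terms reported in one child each. The distinct-child count is then the figure a safety reader wants.

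**Working it through.** No design figure is involved, so the check is of the specification, followed by a short bound.

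**Step 1. Does the specification of 14.3.1.10 contain a category level?** The text of 14.3.2 names SOC and PT as the display levels. The parent shell has those levels plus one any-event row. The footnote defines counting once per patient for SOC and PT only. There is no row, block or counting rule per search.

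**Step 2. Is a repeat by category implied?** Where the SAP wants a shell repeated, it says so. Programmer notes under Tables 14.3.5.1.2, 14.3.5.4 and 14.3.5.5 tell the programmer to continue or repeat the shell for each parameter. Table 14.3.1.10 has no such note.

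**Step 3. Does another planned table give the search count?**

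| Search | Nearest planned count | Is it a count of children found by the search? |
|---|---|---|
| Injection site | SAP 14.3.1, item 6 of the overview | Yes in the text; the 14.3.1.1 shell shows only one injection-site row |
| Hemodynamic | AESI row of the overview, Table 14.3.1.3, Listing 16.2.7.3 | No: AESIs follow Protocol 8.1 (clinical signs, vital signs, investigator judgement) |
| QT | QTcF thresholds, Tables 14.3.5.1.3 and 14.3.5.1.4 | No: measurements |
| Hepatic | Out-of-range chemistry; liver-injury risk as an other important event, Table 14.3.1.4 | No |
| Renal | Out-of-range chemistry | No |
| Allergic | None found | No |

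Allergic, QT, renal, hepatic and searched hemodynamic events therefore have a search-based patient count in 0 of 5 cases.

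**Step 4. Can the count be recovered from PT rows?** Let one search have PT rows with a1, ..., ak children in an arm of n. The number of distinct children D satisfies

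max(ai) ≤ D ≤ min(n, a1 + ... + ak).

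The lower bound is reached when the same children appear on every row, the upper when no child appears twice.

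- Four PT rows of one child each, n = 20: max = 1 and min(20, 4) = 4, so D is 1 to 4. 1/20 = 5% and 4/20 = 20%.
- Three PT rows of two children each, n = 20: max = 2 and min(20, 6) = 6, so D is 2 to 6. 2/20 = 10% and 6/20 = 30%.

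**Step 5. Do SOC counts help?** The text and footnote plan a once-per-patient count at SOC level, although the shell leaves SOC rows without figures. If all terms of one search sit in a single SOC and no other search contributes to it, the SOC count gives D. If the four terms sit in four SOCs, each SOC count is 1 and the range stays 1 to 4. The any-event row settles it only if no other searched event occurred in that arm.

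**The case against.** The strongest reply is that this is a one-line placeholder, not a decision. The SAP lists the searches under separate headings, and the title of 14.3.1.10, unlike those of several neighbouring tables, does not mention SOC and PT. Appendices A and C let programmers reorganise or split tables, and Appendix C says that minor changes to the index need no SAP amendment. All adverse events are listed by patient with MedDRA coding (Listings 16.2.7.1 and 16.2.7.2). With about 40 children, a category can be counted by hand once the term lists are known.

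Much of this stands. The SAP nowhere says that the nine searches are pooled. A reader might infer that from the single category, the single table and the repeated shell, but it remains an inference. The narrower statement, that no category row is specified, does not depend on it. The latitude to reorganise permits the better layout but does not plan it. Listings allow reconstruction, but no search flag is specified for them. The related counts in the table above mean that a hemodynamic, QT, hepatic or renal signal would not go unseen. They answer different questions from the searches.

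A reader might also infer that the any-event row would be dominated by hypoglycemia, since the clamp induces it in every child. The documents do not support that. Under Protocol 8.4, hypoglycemia at the dosing visit is reported as an adverse event only below 54 mg/dL or where IV glucose is given after trial product. Dosing requires plasma glucose of at least 54 and below 80 mg/dL (Protocol 7.4.5.2.2), and SAP 14.3 restricts the table to events that start after dosing or worsen. The documents give no rate for such events.

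**Conclusion.** The point holds as a gap in the planned summaries. Followed as written, the SAP produces no summary table with the number of children who had at least one allergic, QT, renal, hepatic or searched hemodynamic event. The resulting uncertainty can be 1 to 4 children out of 20 (5% to 20%) when four single-child terms of one search lie in different SOCs. That range rests on two assumptions that the documents cannot confirm: that a search spans several PTs and SOCs, and that events fall this way. MedDRA query contents and the external term files are not included.

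The gap concerns the display of descriptive safety data. The underlying events are still collected, coded and listed, and no test, sample size or efficacy conclusion depends on it. It is worth correcting because the better summary is almost free.

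**What to change.** Respecify Table 14.3.1.10 by search category and then PT. Give each of the nine categories a header row with children having at least one event (n, %) and the number of events, by treatment received, as the safety analysis set already requires. List the PTs beneath, and let a PT appear under every search it belongs to. Add to the footnote that a child is counted once per category.

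The cost is one table-shell edit. Search membership has to be derived in any case to select the events for this table. Settle the layout before unblinding, because SAP Section 6 treats analyses performed after that point as post hoc.
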